determining final diagnoses. The tests will include a vestibular exam by a neuro-otologist, repeat VOG, caloric testing, formal audiology, and MRI as applicable. The timing of the Week-1 visit will be determined based on optimal MRI sensitivity for detecting stroke and logistical constraints. The optimal MRI timing window for diffusion-weighted images to detect stroke is roughly 3-7 days after the onset of continuous dizziness or vertigo symptoms, although MRI-DWI detects acute stroke with high sensitivity out to 14 days or longer. We will define “T0” (time zero) as the time when dizziness symptoms began or most recently worsened, leading to the ED index visit. We will define “T1” as the ED registration time at the ED index visit. Follow-up MRI should not occur prior to 72 hours after ‘T0’ to reduce the odds of a false negative follow-up MRI scan for those with stroke. The target window for MRI is 3-7 days after T0, but up to 14 days will be considered acceptable for the purposes of inclusion in the primary outcome analysis (see Statistical Analysis Plan below). If T0 is unknown or uncertain, we will use time from T1 to determine the appropriate follow-up window. For scheduling purposes, the 1-week follow-up testing may be performed over two half days, separated in time. Regardless of exact timing, this visit will be known as the “1-Week” or “Week-1” follow-up visit.

6.2.4 30-Day Phone Follow-up: All subjects will complete a phone interview 30 days (+/- 7 days) after the ED Index Visit. In the event that no 6-month follow-up is possible (e.g., due to funds limitations), the subject will be instructed that this is the final visit. 30-day phone follow-up (~20-30 min) will repeat symptom and quality-of-life measures (see Schedule of Evaluations) and determine hospitalizations or doctor visits for stroke-related diagnoses (e.g., stroke, aneurysm, heart attack). We will review relevant medical records for vascular events, outpatient visits (particularly neurology or otolaryngology), ED visits, hospitalizations, and neuroimaging. Regardless of exact timing, this visit will be known as the “30-Day” or “1-Month” follow-up visit.

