Analytic approach: For all primary and linked secondary analyses, we will include only randomized subjects completing the essential elements of the diagnostic study protocol through the end of 1-week follow-up (i.e., with ED index visit VOG test results, follow-up MRI within 14 days, and an in-person neuro-otology visit within 30 days of the index visit). The quality of VOG and MRI testing will be determined by masked, expert raters from the FDAC during an FDAC meeting pre-review process; if either essential test is deemed to be of insufficient quality for analysis (e.g., key VOG tests performed improperly or missing; motion artifact on MRI), such patients will be excluded from the primary and linked secondary analyses of the main trial outcomes. This per-protocol analysis is appropriate for this Phase II study designed to determine the potential efficacy of the VRT intervention on diagnostic accuracy. Without adequate quality VOG and 1-week follow-up data, diagnoses will remain speculative. Subjects lost to follow-up at the 30-day time point (phone follow-up) will be included in these analyses, as 1-month medical record review will generally be sufficient to determine correct diagnoses.

Definitions: For the purposes of all analyses, the term “stroke” refers to any acute cerebrovascular event (ischemic stroke, transient ischemic attack, intracranial hemorrhage), unless expressly specified otherwise.

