Statistical Analysis Plan 2: Analyses will include two-sample comparisons of mean and median costs. Mean of total cost between two study-arms will be compared by modified t-test with unequal variances. Median total cost between two study-arms will be compared by Wilcoxon-Mann-Whitney tests.¹⁶²

9.2.3 Aim 3 (Observational Outcome): Compare clinical outcomes for correct vs. incorrect diagnoses

Hypothesis 3: ED patients with vertigo or dizziness who receive standard care will have better outcomes if correctly diagnosed than if misdiagnosed (*this is an observational outcome in the standard-care arm*).

Primary Outcome 3: Proportion with short-term serious medical events (SMEs) occurring between the time of ED index visit disposition and 1-week research follow-up visit among those with correct vs. incorrect ED provider Diagnosis. “Correct” vs. “incorrect” diagnoses are categorized in one of six possible diagnosis categories (3 peripheral, 1 central, 1 medical/other, 1 non-diagnosis). SMEs will include ED revisits, falls, hip fractures, vascular events (including stroke), and test or treatment complications.

Statistical Analysis Plan 3: A multivariable logistic regression will be used to estimate the odds of an SME (correct diagnosis vs. misdiagnosed) adjusting for demographic and clinical variables.

Specifically, define $S_i = 1$ if the i th subject experience SMEs between the time of ED index visit disposition and 1-week research follow-up visit. Following notation used in Aim 1, define the logistic model as,

$$\text{logit } P(S_i = 1 | X_{Test} = 0) = \beta_0 + \beta_1 Y_i(0) + \overline{\beta_2} \cdot \overline{Z_i}$$

where $Y_i(0)$ is the variable indicating correct or incorrect diagnoses in SOC arm as defined in aim 1, $\overline{Z_i}$ are additional subgroups variables or other covariates listed in Aim 1.

In addition, standard time-to-event analyses (Kaplan-Meier,¹⁶³ Cox regression¹⁶⁴) will be used to estimate relative hazard ratios, adjusting for demographic and clinical variables listed in Aim 1.

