2. STATISTICAL ANALYSIS PLAN

2.1 General Design Issues

Main trial design: Randomized controlled trial (individual patient randomization), parallel design (1:1). Results will be used for primary outcome analyses related to diagnosis accuracy at the ED index visit.

Secondary cohort design: Cohorts will be followed for adverse events and functional outcomes (1wk, 30d). Estimates will be used for phase 3 trial planning for the impact of diagnosis accuracy on clinical events and outcomes. The 6-month follow-up time point (if available) will not be part of the primary trial outcomes.

Observational arm: Patients with vestibular symptoms but no signs or who are not randomized for other reasons (see Inclusion and Exclusion Criteria) will be eligible for a parallel track observational sub-study with limited phone follow-up.

Diagnosis adjudication: Prior to adjudication, index VOG results will be interpreted by two independent vestibular experts masked to allocation. They will be given only patient demographic information, a structured summary of dizziness-related history of the present illness, and bedside hearing test results. Using this information, and masked to all other index visit clinical findings, ED physician diagnoses, any neuroimaging, and all follow-up data, they will render an ED index visit diagnosis (“Index VOG Diagnosis”). Prior to adjudication, MRIs will be interpreted by two independent neuro-radiologists masked to allocation and all clinical findings other than demographic information. They will render an index visit diagnosis (“Index Radiology Diagnosis”). A 5-member multidisciplinary panel with ED physician, otolaryngologist, vestibular neurologist, stroke neurologist, and neuro-radiologist will adjudicate diagnoses. The panel will be masked at all times to trial allocation (VRT vs. standard care). Diagnoses will be classified into 1 of 6 diagnostic categories likely to affect ideal ED management and rated as probable or definite based on neuroimaging results and standard clinical criteria. Diagnoses will be rendered in two stages – first based on VOG and all clinical data (including eye videos) from the ED index visit alone, without follow-up data (“Adjudicated Index Diagnosis”); then again after all 1-week testing and 30-day follow-up data are revealed electronically (“Adjudicated Final Diagnosis”). All differences will be resolved by discussion or majority vote.

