2.2 Outcomes

2.2.1 Aim 1 (Trial Outcome): Measure the impact of VRT on diagnosis and initial management

Hypothesis 1: The VRT pathway will yield more correct diagnoses by the end of the ED index visit than the standard care (ED provider-determined) pathway.

Primary outcome 1: Six-Category Diagnosis Accuracy (all, VRT vs. SOC). Total proportion of correct diagnoses made by VRT vs. SOC among subjects with 30-day adjudicated final diagnoses (the gold standard) categorized in one of six possible diagnosis categories (3 peripheral, 1 central, 1 medical/other, 1 non-diagnosis).

Statistical Analysis Plan 1:

Primary analysis 1: A generalized linear model with a log link will be used for comparing the true positive rates (TPRs) of VRT and SOC. Without additional covariates, the model-based score test is equivalent to a Pearson Chi-square test for unpaired data. The regression model will assess the influence of demographic and key clinical variables as exploratory subgroups. Generalized estimating equation (GEE)¹⁶¹ method will be used to account for clustering effects by hospital site or provider. VOG non-completers are excluded pre-randomization (randomization occurs post-VOG for all patients).

Specifically, define $D_i = 1$ if the 30-day adjudicated final diagnosis for the i th subject is categorized in one of six possible diagnosis categories (3 peripheral, 1 central, 1 medical/other, 1 non-diagnosis). Define a test variable as

$$X_{Test} = \begin{cases} 1 & \text{for VRT} \\ 0 & \text{for SOC} \end{cases}$$

Define $Y_i(\text{VRT}) = 1$ if the index VRT diagnosis for the i th subject is the same as his/her 30-day adjudicated final diagnosis and $Y_i(\text{VRT}) = 0$ otherwise. Similarly, define $Y_i(\text{SOC}) = 1$ if the ED SOC Diagnosis for the i th subject is the same as his/her 30-day adjudicated final diagnosis and $Y_i(\text{SOC}) = 0$ otherwise.

The TPR, over the total proportion of correct diagnoses, is defined as follows

$$TPR(X_{Test}) = P[Y_i(X_{Test}) = 1 | D_i = 1], \quad X_{Test} = 0, 1.$$

Define the regression model as

$$\log TPR(X_{Test}) = \alpha_0 + \alpha_1 X_{Test} + \overline{\alpha_i} \cdot \overline{X_i}$$

where $\overline{X_i}$ is a vector of additional subgroup variables or other covariates to be explored for assessing the influence of demographic and key clinical variables described in the secondary analysis.

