Hypothesis 2: The VRT pathway is cost saving relative to current ED practice in diagnostic assessments.

Primary outcome 2: Total dollar costs of VRT as compared to SOC for diagnostic tests and consultations obtained during the ED index visit and hospital admission (for those admitted at the index visit). The cost for VRT arm does not include the costs of protocol safety MRIs or any tests not specified by the pathway but ordered for clinical purposes by ED providers. It does include tests ordered as part of the VRT pathway by consultants or ED providers in the “equivocal” pathway. Total costs will be calculated by multiplying fixed cost estimates (most recent year available average Medicare reimbursement in US dollars) by utilization rates for each ED index visit service tracked.

Statistical Analysis Plan 2: Analyses will include two-sample comparisons of mean and median costs. Mean of total cost between two study-arms will be compared by modified t-test with unequal variances. Median total cost between two study-arms will be compared by Wilcoxon-Mann-Whitney tests.¹⁶²

2.2.3 Aim 3 (Observational Outcome): Compare clinical outcomes for correct vs. incorrect diagnoses

Hypothesis 3: ED patients with vertigo or dizziness who receive standard care will have better outcomes if correctly diagnosed than if misdiagnosed (*this is an observational outcome in the standard-care arm*).

Primary Outcome 3: Proportion with short-term prespecified medical events of interest (PMEIs) occurring between the time of ED index visit disposition and 1-week research follow-up visit among those with correct vs. incorrect ED SOC diagnosis. “Correct” vs. “incorrect” diagnoses are categorized in one of six possible diagnosis categories (3 peripheral, 1 central, 1 medical/other, 1 non-diagnosis). PMEIs will include ED revisits, falls, vascular events (including stroke), and test or treatment complications.

Statistical Analysis Plan 3: A multivariable logistic regression will be used to estimate the odds of an PMEI (correct diagnosis vs. misdiagnosed) adjusting for demographic and clinical variables.

Specifically, define $S_i = 1$ if the i th subject experience PMEIs between the time of ED index visit disposition and 1-week research follow-up visit. Following notation used in Aim 1, define the logistic model as

$$\text{logit } P(S_i = 1 | X_{Test} = 0) = \beta_0 + \beta_1 Y_i(0) + \overline{\beta_2} \cdot \overline{Z_i}$$

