where $Y_i(0)$ is the variable indicating correct or incorrect diagnoses in SOC arm as defined in Aim 1, $\overline{Z_i}$ are additional subgroups variables or other covariates listed in Aim 1.

In addition, standard time-to-event analyses (Kaplan-Meier,¹⁶³ Cox regression¹⁶⁴) will be used to estimate relative hazard ratios, adjusting for demographic and clinical variables listed in Aim 1.

Exploratory Outcomes:

1. Preventable Six-Category Diagnosis Error (all, VRT vs. SOC)

Total diagnosis inaccuracy (error) VRT vs. SOC using adjudicated index diagnoses categorized in one of six diagnosis categories (3 peripheral, 1 central, 1 medical/other, 1 non-diagnosis). Adjudicated index diagnoses will be determined using only ED index visit data that “would have been” available clinically (i.e., excluding safety MRI, index hospital admission data, and all follow-up data).

2. VRT vs. MRI Stroke-No Stroke Diagnosis Accuracy (VRT arm only, VRT vs. MRI)

Total diagnosis accuracy VRT vs. index imaging using 30-day adjudicated final diagnoses categorized as stroke vs. no stroke (posterior fossa mass lesion, encephalitis, etc.). The VRT arm is chosen here because all VRT arm patients will undergo MRI at the index visit (protocol, clinical, or safety), eliminating diagnostic ascertainment bias that may be present in the SOC arm.

3. Algorithm-Only VRT Six-Category Diagnosis Accuracy (all, initial VRT output vs. SOC)

Total diagnosis accuracy “as computed in real time,” algorithm-only VRT diagnosis vs. SOC using 30-day adjudicated final diagnoses categorized in one of six diagnosis categories (3 peripheral, 1 central, 1 medical/other, 1 non-diagnosis). We will use “Index VRT Diagnosis” and “ED SOC

Diagnosis" compared to the "Adjudicated Final Diagnosis" based on ED index visit and 30-day follow-up clinical assessments. This outcome measure reflects the weighted average diagnostic accuracy of the various versions of the automated algorithm as it would have been absent human double-check during the course of the trial.

4. Optimized Six-Category Within-Subject Accuracy (SOC arm only, optimized VRT vs. SOC)

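### Aim 3 labels the ED diagnosis correct or incorrect using an adjudication that has seen the outcome events, so the exposure can depend on the outcome

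*SAP*

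**What the plan says.** The exposure, the reference diagnosis and the outcome are defined in different places.

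- **Exposure.** The Aim 3 logistic model (SAP 2.2.3) regresses the event indicator on Y_i(0), which "is the variable indicating correct or incorrect diagnoses in SOC arm as defined in Aim 1". Aim 1 (SAP 2.2.1) sets that variable to 1 "if the ED SOC Diagnosis for the i th subject is the same as his/her 30-day adjudicated final diagnosis".
- **Reference diagnosis.** Under SAP 2.1 the panel adjudicates twice. The first pass uses index-visit data alone and gives the Adjudicated Index Diagnosis. The panel decides "then again after all 1-week testing and 30-day follow-up data are revealed electronically", which gives the Adjudicated Final Diagnosis. Aim 3 uses the second.
- **Content of follow-up.** Protocol 6.2.4 says of the 30-day contact: "We will review relevant medical records for vascular events, outpatient visits (particularly neurology or otolaryngology), ED visits, hospitalizations, and neuroimaging". Protocol 9.1 keeps patients who miss the 30-day call in the primary and linked secondary analyses, "as 1-month medical record review will generally be sufficient to determine correct diagnoses".
- **Outcome.** The SAP counts prespecified medical events of interest (PMEIs) "occurring between the time of ED index visit disposition and 1-week research follow-up visit" and compares them "among those with correct vs. incorrect ED SOC diagnosis". They are ED revisits, falls, vascular events including stroke, and complications of tests or treatment. The protocol has the same structure under the name of serious medical events: "SMEs will include ED revisits, falls, hip fractures, vascular events (including stroke), and test or treatment complications".
- **Masking.** SAP 2.1 and Protocol 4.3.7 mask the panel to trial arm. Neither mentions masking to PMEIs.

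**The concern.** A cohort comparison needs an exposure that is fixed without knowledge of the outcome. Here the outcome window, from disposition to the 1-week visit, lies wholly inside the data shown to the panel before it fixes the reference diagnosis. Suppose a patient is sent home with a peripheral diagnosis and has a stroke on day 4. That patient contributes a PMEI. If the panel reads the stroke as the cause of the index dizziness, the same event also makes the ED diagnosis incorrect. The planned Cox analysis names no other exposure, so it would carry a baseline label set from data later than its own time origin.

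Aim 3 estimates are meant for Phase III planning (SAP 2.1, secondary cohort design). With few events expected, one or two adjudications could decide the odds ratio that is carried forward.

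**Working it through.** **1. The plan's own figure.** The standard-care arm has 113 patients (SAP 2.3, 90% vs. 75%, alpha 0.05, power 80%). The two-sided formula gives n = [1.960·√(2·0.825·0.175) + 0.842·√(0.90·0.10 + 0.75·0.25)]² / 0.15² = 99.5. The continuity correction, (n/4)·[1 + √(1 + 4/(n·0.15))]², gives 112.5, so 113. The figure reproduces. No event rate, effect size or power is stated for Aim 3.

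**2. Inputs.** From the documents: n = 113, and standard-care accuracy of 75% (planning value) or about 56% (the best estimate cited in SAP 2.3). Assumed: PMEI rates of 5%, 10% and 20%, and the number of patients re-labelled because of an event. The full 113 is an upper limit if Aim 3 follows the completer rule of Protocol 9.1.

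**3. Null table at 75% accuracy.** Expected numbers are 113 × 0.75 = 84.75 correct and 28.25 incorrect, with the same event rate in both. Let E_c and E_i be the expected events in each group. Moving a net k patients with an event from correct to incorrect leaves the event-free counts alone, and their ratio is 84.75/28.25 = 3. The odds ratio for incorrect vs. correct is therefore

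OR = 3 × (E_i + k) / (E_c − k).

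| PMEI rate | E_c | E_i | OR, k = 0 | OR, k = 1 | OR, k = 2 | k = 2 as share of E_c |
|---|---|---|---|---|---|---|
| 5% | 4.24 | 1.41 | 1.00 | 2.24 | 4.58 | 47% |
| 10% | 8.48 | 2.83 | 1.00 | 1.54 | 2.24 | 24% |
| 20% | 16.95 | 5.65 | 1.00 | 1.25 | 1.54 | 12% |

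For example, at 10% with k = 2: 3 × 4.825/6.475 = 2.24. The SAP codes Y = 1 as correct, so its own odds ratio would be the reciprocal.

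**4. Flips in both directions.** Let f be the share of events in ED-correct patients that turn the label to incorrect, g the share of events in ED-incorrect patients that turn it to correct, and p the accuracy. Then

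OR = [(1−p)(1−g) + p·f] / [p(1−f) + (1−p)·g] × p/(1−p),

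whatever the PMEI rate.

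| f | g | OR, p = 0.75 | OR, p = 0.56 |
|---|---|---|---|
| 10% | 0 | 1.44 | 1.25 |
| 25% | 0 | 2.33 | 1.76 |
| 25% | 25% | 1.80 | 1.13 |
| 10% | 25% | 1.07 | 0.80 |

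**5. Effect on a test.** This comes from a simulation with 20,000 replicates, 113 patients, a 10% PMEI rate, 75% accuracy, no true effect and an unadjusted test at 0.05. With f = 25% and g = 0 (about 2 of 8.5 events), the false-positive rate is 25.9% by likelihood-ratio test and 23.1% by Fisher's test. With no re-labelling it is 6.9% and 2.7%.

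**The case against.** **Some re-labelling is correct.** A stroke within days of a peripheral discharge often means that the ED missed the index cause, which is the pathway Aim 3 sets out to study. Bias arises only when a new event is wrongly attributed to the index episode. This stands, and the null tables above do not separate the two cases.

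**The common work-up limits the feedback.** Protocol 9.1 restricts the primary and linked secondary analyses to patients with a follow-up MRI within 14 days and an in-person neuro-otology visit. Most categories can therefore be settled without reference to an event. This stands in part. The MRI comes after disposition, and standard-care patients have no required index MRI (Protocol Table 1). Reports also word prior imaging so that the panel cannot tell whether any existed (Protocol 4.3.7). A new stroke may thus be read as the index cause. The Protocol 9.1 definition of stroke includes TIA, which can rest on later history.

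**Three stronger readings are tempting, and the documents do not support them.**

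- A reader might infer that the bias must favour Hypothesis 3. An event can also confirm an ED central diagnosis, and the last row of step 4 shows an odds ratio near or below 1.
- A reader might infer that any PMEI can change the label. A fall or a complication would rarely change a diagnostic category, and a revisit does so only through new diagnostic information.
- A reader might infer that the decision to proceed to Phase III is compromised. That rule uses Aims 1 and 2 only (SAP 2.3). Aim 1 does not have this problem, since PMEIs are not its outcome.

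**Conclusion.** The structural point holds. Aim 3 takes its exposure from an adjudication that sees the outcome events, and nothing in either document blocks the feedback. The realistic routes are stroke or TIA and diagnostic revisits. Bias towards Hypothesis 3 is likely but not certain.

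The size cannot be derived from the documents. The odds ratios of 1.25 to 4.58 for one or two net re-labels rest on 113 patients, 75% accuracy, no true effect and assumed PMEI rates of 5% to 20%. The 4.58 requires nearly half of the events in ED-correct patients to be re-labelled. What the figures do show is fragility: at a 10% rate about 11 events are expected (113 × 0.10 = 11.3), so very few adjudications can move the estimate materially. This is a flaw worth correcting in an observational aim. It does not touch the randomised comparison.

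**What to change.** In SAP 2.2.3, pre-specify a sensitivity analysis that repeats the Aim 3 logistic and Cox models with correct/incorrect defined against the Adjudicated Index Diagnosis. That diagnosis is already made without follow-up data, and the SAP now uses it only for Exploratory Outcome 1. Report the two versions side by side. If they differ materially, describe the association as not robust to outcome-informed adjudication, and carry both estimates into Phase III planning.

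Two stricter measures are not advisable. Requiring an association to hold in every version would be uninformative with about 11 events: at a 10% rate and 75% accuracy, Fisher's test has roughly one chance in six of detecting a true odds ratio of 2, and little more than one in three for 3. Removing strokes that determined the final diagnosis would delete the harm under study, and no passage says that the panel records which evidence decided a case.

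The cost is a little extra analysis, since both adjudicated diagnoses are already planned. The drawback is a weaker reference. The index diagnosis lacks the 1-week MRI and vestibular tests, so it may call some truly missed strokes correct and pull the odds ratio towards 1. A difference between the two versions therefore signals lack of robustness and does not show that there is no effect.

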Secondary analysis 1: For each of the six possible diagnosis categories (3 peripheral, 1 central, 1 medical/other, 1 non-diagnosis), define the gold standard =1 if the 30-day adjudicated final diagnosis is the corresponding category and 0 otherwise. Define test positive respectively for “Index VRT Diagnosis” and “ED SOC Diagnosis” if the diagnosis is the corresponding category and 0 otherwise. Estimate sensitivity, specificity, predictive values and likelihood ratios accordingly for “Index VRT Diagnosis” and “ED SOC Diagnosis”. Between-arm comparisons will be performed by the generalized linear model with a log link as described in primary analysis 1a.

Tertiary analysis 1: Subgroups and covariates:

The regression model is

$$\log TPR(X_{Test}) = \alpha_0 + \alpha_1 X_{Test} + \overline{\alpha_l} \cdot \overline{X_l}$$

where $\overline{X_l}$ is a vector of additional subgroup variables or other covariates to be explored for assessing the influence of demographic and key clinical variables described below.

1) Potential Subgroups:

- a. AVS-Only Group: using only patients with acute (continuous) vestibular syndrome >24hr.
- b. Younger-Patient Group: using only patients 49 years of age or younger (i.e., 18-49).
- c. Women-Minority Group: using only patients self-identifying as female, minority, or Hispanic.
- d. NIHSS 0 Group: using only patients with an NIH stroke scale score of zero at ED index visit.
- e. Stands-Independently Group: using only patients who stand without assistance or support.
- f. Normal Hearing Group: excluding any patient with hearing loss (new or old).
- g. Non-AICA Group: excluding any patient with an AICA-territory stroke diagnosis.
- h. Pre-Treatment Group: using only patients with results obtained prior to anti-vertigo meds.
- i. VRT Definite-Only Group: using only “definite” VRT diagnoses (excluding VRT-E cases).
- j. Specific ED-Only Diagnosis Group: using only “definite” ED diagnoses (excluding ED O2).
- k. Neuro-otologic Diagnosis Group: using only patients with peripheral or central diagnoses.

2) Potential Covariates:

- l. Site: JH vs. UI vs. UM.
- m. Age (ordinal): 18-49, 50-59; 60+ years.
- n. Age (continuous): for each year.
- o. Sex: female vs. male.
- p. Race/Ethnicity: minority vs. non-Hispanic white.
- q. Symptom Onset (ordinal): 0-24, 25-48, 49-72, >72 hours.
- r. Symptom Onset (continuous): time from symptom-onset for each hour.
- s. Symptom Type: vertigo vs. dizziness vs. unsteadiness.

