2.3 Sample Size and Accrual

Powering Endpoint: AVERT will be powered to detect a clinically important difference in diagnosis accuracy of 90% vs. 75% (113 per arm). VRT diagnosis is anticipated to be nearly 100% accurate. We have shown that expert eye movement exams have 98.4% (n=187/190) accuracy for differentiating peripheral (vestibular neuritis) from central (stroke) vestibular disorders in acute, continuous vertigo.⁷³ We have now replicated these findings with the VOG device in 21 acute vertigo patients (100% accuracy). The gold standard for BPPV diagnosis is eye movement analysis,^{48,78} often by VOG,^{51,165} so we conservatively estimate that VOG accuracy across all vestibular conditions will be >90%. Diagnosis accuracy of routine ED care varies, estimated at <20% for BPPV and neuritis⁵ and ~70% for stroke, and lower (~50%) if stroke presents with isolated vertigo.^{7,135,136} Best estimates suggest an

Table 3. Comparison of proportions power estimate (alpha 0.05, power 80%)

VOG Care Correct Diagnoses	Standard Care Correct Diagnoses	Per-arm sample (total study sample)
99%	50%	15 (30)
95%	50%	19 (38)
90%	50%	25 (50)
99%	75%	38 (76)
95%	75%	59 (118)
90%	75%	113 (226)

overall correct ED diagnosis rate of about 56% for vestibular patients.¹¹⁴ In EDs with greater access to specialty consultations or frequent MRI neuroimaging, the proportion of correct diagnoses may range higher. We have powered the AVERT Trial for an anticipated worst-case scenario of 90% VOG accuracy and 75% standard care accuracy (Table 3).

Recruitment Capacity: Our 3-site consortium has a total of ~180,000 ED visits per year. Chief symptoms of vertigo/dizziness account for ~3-4% of ED visits.^{15,123} Thus, our 3 sites have ~5,400-7,200 ED dizziness visits per year (~5-7 patients per 24hrs per site). Of these, we estimate ~20-30%²⁰ will meet inclusion criteria (~1-2 patients per 24hrs per site). We will screen during five designated 7-hr shifts weekly, performing VOG on ~3-5 patients per week, enrolling ~2-4 patients per month per site, taking ~3 years to reach 226.

Number of Strokes: With our inclusion criteria, we expect ~10-20% strokes (n=11-23 per arm). This will not yield firm conclusions about VOG stroke accuracy, but should be sufficient for phase 3 trial planning.

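### The Aim 3 logistic and Cox models draw their adjustment set from 18 potential covariates (25 parameters) with no subset or limit named, more than at most 113 standard-care patients can support

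*SAP*

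**What the plan says.** SAP 2.2.3 sets Primary Outcome 3 as the proportion of patients with a prespecified medical event of interest (PMEI) between ED disposition and the 1-week visit, compared by whether the ED diagnosis was correct. The SAP notes that "this is an observational outcome in the standard-care arm".

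The logistic model has an intercept, a term for correct diagnosis, and a vector Z whose elements "are additional subgroups variables or other covariates listed in Aim 1". Kaplan-Meier and Cox analyses follow, the Cox model "adjusting for demographic and clinical variables listed in Aim 1". Protocol 9.2.3 has the same model, with serious medical events in place of PMEIs.

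The list pointed to is in SAP 2.2.1, Tertiary analysis 1. It has 11 potential subgroups (a to k) and 18 potential covariates (l to cc), introduced as variables to be explored. Age appears as "Age (ordinal): 18-49, 50-59; 60+ years" and again per year. Symptom onset appears in four bands and again per hour. Stroke size and stroke location are also listed.

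For Aim 3, neither document names a subset, a selection rule, a ceiling tied to the number of events, or a method for sparse data. Neither gives a PMEI rate or a power calculation for this aim.

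**The concern.** The pointer sends the analyst to a list written to explore the Aim 1 accuracy model in both arms, and applies it to an observational comparison in one arm with an unknown and possibly small number of events. Two things can then go wrong.

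- If the full list is fitted, ordinary maximum likelihood has too few events for the parameters. The coefficient for correct diagnosis can diverge, or be finite but far from the truth with an interval that is too narrow.
- If the list is treated as a menu, the adjustment set for a stated primary outcome is chosen after the data are seen, and no rule limits the choice.

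Stroke size and location add a separate problem. In the standard-care arm the only MRI that the study requires is the 1-week research scan (Protocol Table 1), at the end of the event window. These variables may therefore postdate the diagnosis being studied. They may also overlap with the outcome, since PMEIs include stroke.

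SAP 2.1 says that the cohort estimates will feed phase 3 planning, so an unreliable odds ratio here has a use downstream.

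**Working it through.** **Sample size.** SAP 2.3: "AVERT will be powered to detect a clinically important difference in diagnosis accuracy of 90% vs. 75% (113 per arm"). For 0.90 vs 0.75, two-sided alpha 0.05, power 80%, with mean proportion 0.825:

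n = [1.96·√(2·0.825·0.175) + 0.842·√(0.90·0.10 + 0.75·0.25)]² / 0.15² ≈ 99.5, so 100 per arm.

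With continuity correction: (99.5/4)·[1 + √(1 + 4/(99.5·0.15))]² ≈ 112.5, so 113.

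The plan's figure reproduces, as do all six rows of Table 3. It contains no allowance for loss. Protocol 9.1 limits the main comparisons, and those tied to them, to completers: "we will include only randomized subjects completing the essential elements of the diagnostic study protocol through the end of 1-week follow-up". Whether Aim 3 follows that rule is not stated; if it does, 113 is an upper limit. The Protocol 6.1 schedule also marks index-visit VSS-SF and Charlson scores, both on the list, as time permitting.

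**Parameters.** Site 2, age bands 2, age in years 1, sex 1, race/ethnicity 1, onset bands 3, onset in hours 1, symptom type 2, VSS-SF 1, syndrome 2, hearing loss 1, ABCD2 1, NIHSS 1, SARA 1, stroke size 1, stroke location 2, confounded 1, Charlson 1. Sum = 25, or 26 slopes with the diagnosis term. Dropping the banded codings of age and onset leaves 20, or 21 slopes. The 11 subgroup variables are not counted.

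**Events per parameter.** For the logistic model, the ratio is min(events, non-events) / slopes.

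- Ceiling at any event rate: 56/26 = 2.2.
- Assumed 5%: 5.65/26 = 0.22.
- Assumed 10%: 11.3/26 = 0.43.
- Assumed 20%: 22.6/26 = 0.87.

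The ceiling is specific to the logistic model. A Cox model counts events only, so its limit would be 113/26 = 4.3 if every patient had an event. At 5–20% its ratios are the same as above.

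**Simulation.** N = 113, true odds ratio 0.5, and 56% or 75% correctly diagnosed (the SAP 2.3 best estimate and powering value). Covariate distributions were assumed; 600–1,000 data sets per cell.

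| Event rate (assumed) | Full list: any coefficient separated | Full list: diagnosis coefficient infinite | Three covariates: any separated |
|---|---|---|---|
| 5% | over 99% | 91–92% | 19–20% |
| 10% | 91–93% | 38–39% | 1–2% |
| 20% | 59–62% | 1% or less | 0% |

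A second simulation, counting a failed fit or a diverging diagnosis coefficient, gave about 88%, 39% and 1%.

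At 20% events, among full-list fits without separation, the standard deviation of the log odds ratio was 1.08–1.17, against a median model standard error of 0.70–0.77. The central 95% of estimated odds ratios ran from about 0.03 to between 1.8 and 3.9, for a true value of 0.5. With three covariates the standard deviation was 0.53–0.59: 1.08/0.53 = 2.0 and 1.17/0.59 = 2.0.

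Removing the duplicate codings is not enough: at 10% events, 85–89% of data sets still showed some separation.

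**The case against.** The strongest reply is that the SAP never commits to fitting everything. The covariates are headed as potential and are to be explored, and two codings of the same variable suggest alternatives. One subgroup item, definite VRT diagnoses only, has no trial-time value in standard care, where no VOG report is generated. This stands: a reader might infer that all 18 enter jointly, and the text does not say so. It does not close the gap, because a menu without a selection rule leaves the adjustment set undefined.

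Other parts of the reply also stand.

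- **Event count.** The 5–20% range, about 6 to 23 events, is assumed. PMEI is a broad composite, and nothing in the documents caps it at 20%.
- **Sensitivity to assumptions.** In a null simulation with 25 independent normal covariates and 20% events, the share of odds ratios off by more than 3-fold fell from 33% with 25% misdiagnosed to 21% with 44% misdiagnosed. At 40% events with 44% misdiagnosed it was 8%.
- **Source of the gain.** With two covariates at 20% events and 25% misdiagnosed, ordinary maximum likelihood gave 7% and Firth 6% on that measure. Nearly all the improvement comes from fewer covariates. Firth matters mainly at low counts: at 5% events, even the three-covariate model had an infinite diagnosis coefficient in about 12% of data sets.
- **Confounding.** The simulations contained none, so a smaller model was bound to do better. The price of leaving out a real confounder was not measured.
- **Stakes.** The adjusted odds ratio is not Aim 3's only output: the outcome is a pair of proportions, and Kaplan-Meier and Cox analyses are planned. The SAP 2.3 rule for proceeding to phase 3 uses Aims 1 and 2 only.

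**Conclusion.** The point holds in a limited form and is a cheap improvement. The Aim 3 adjustment set is not prespecified, and the only list it points to is too large for the arm. The ceiling of about 2.2 events per parameter in the full logistic model needs only the 113 patients and the 26 slopes. The 0.2–0.9 range rests on an assumed PMEI rate of 5–20%.

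Under the simulated conditions, the full-list diagnosis odds ratio would usually diverge at 5% events and in over a third of data sets at 10%. At 20% it would rarely diverge, but its log-scale standard deviation would be about twice that of a model with two or three covariates, and its stated precision too good. These percentages depend on assumed covariate distributions.

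Two stronger readings are not supported. One is that the diagnosis odds ratio would be separated across the whole assumed range; at 20% events the separation is almost all in other coefficients. The other is that the trial's main conclusion or the phase 3 decision is at risk; neither depends on this model.

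**What to change.** In SAP 2.2.3 and Protocol 9.2.3, replace the pointer to the Aim 1 list with a short, closed specification:

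- Two or three baseline covariates, chosen by the sponsor on clinical grounds before analysis, with one coding each. The documents give no basis for prescribing which ones.
- No stroke size or stroke location.
- Firth penalised logistic regression with profile-likelihood confidence intervals.
- The same covariate set in the Cox model.
- The unadjusted estimate beside the adjusted one, with event counts by diagnosis group. At 5% events the unadjusted model itself separated in 13–14% of simulated data sets, so the counts should always be visible.

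The cost is a few lines of text and less control of confounding in an observational comparison, which the report should state. The fix does not create information: with three single-parameter covariates (4 slopes) there would still be only 1.4, 2.8 and 5.7 events per parameter at 5%, 10% and 20% events.
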